**Error! Reference source not found.: Visit Window**

	Cycle 1			Cycle 2		Cycle 3 and onwards	Last Cycle	Follow-up		
	D1	D8 (±1)	D15 (±1)	D22 (±1)	D1 (±3)	D15 (±3)	D1 (±3)	CXD1	Study Completion or Early Termination (30±7 Days After the End of Treatment)	Follow-up on Day 1 (±7) Quarterly After the End of Treatment
Scheduled Day [a]	1	8	15	22	1	15	1	1		
ECOG performance status	Day1		2 to EOC-3		Day -3 to 8	9 to EOC-3	Day -3 to EOC-3	Day-3 to EOC	Last dose date of last cycle +1 to last dose date of last cycle +37	
Vital signs	Day1	2 to 11	12 to 18	19 to EOC-3	Day -3 to 8	9 to EOC-3	Day -3 to EOC-3	Day-3 to EOC		

HUTCHMED Ltd.

CONFIDENTIAL

HMPL-523

									Follow-up	
	Cycle 1				Cycle 2		Cycle 3 and onwards	Last Cycle		
	D1	D8 (±1)	D15 (±1)	D22 (±1)	D1 (±3)	D15 (±3)	D1 (±3)	CXD1	Study Completion or Early Termination (30±7 Days After the End of Treatment)	Follow-up on Day 1 (±7) Quarterly After the End of Treatment
Hematology		1 to 11	12 to 18	19 to EOC-3	Day -3 to 8	9 to EOC-3	Day -3 to EOC-3	Day-3 to EOC		
Urinalysis/ dipstick			1 to EOC-3		Day -3 to 8	9 to EOC-3	Day -3 to EOC-3	Day-3 to EOC		
Chemistry panel		1 to 11	12 to 18	19 to EOC-3	Day -3 to 8	9 to EOC-3	Day -3 to EOC-3	Day-3 to EOC		
Beta 2-microglobulin					Cycle 1 Day 1 to EOC-3		Day -3 to EOC-3	Day-3 to EOC		
Fasting lipid profile					Cycle 1 Day 1 to EOC-3		Day -3 to EOC-3	Day-3 to EOC		
Serum amylase and lipase		1 to 11	12 to 18	19 to EOC-3	Day -3 to 8	9 to EOC-3	Day -3 to EOC-3	Day-3 to EOC		
Coagulation assay (INR, aPTT, PT)					Cycle 1 Day 1 to EOC-3		Day -3 to EOC-3	Day-3 to EOC		
Leukocyte immunophenotyping			1 to EOC-3		Day -3 to EOC-3		Day -3 to EOC-3	Day-3 to EOC		
Echocardiogram/MUGA										

HUTCHMED Ltd.

CONFIDENTIAL

HMPL-523

								Last Cycle	Follow-up	
	Cycle 1				Cycle 2		Cycle 3 and onwards			
	D1	D8 (±1)	D15 (±1)	D22 (±1)	D1 (±3)	D15 (±3)	D1 (±3)		CXD1	Study Completion or Early Termination (30±7 Days After the End of Treatment)
12-Lead ECG	Day 1-2		3 to EOC -3		Day -3 to EOC -3		Day -3 to EOC -3	Day -3 to EOC		
Quantitative serum immunoglobulin levels (for WM/LPL)					Cycle 1 Day 1 to EOC -3		Day -3 to EOC -3	Day -3 to EOC		X
CT/PET-CT							Cycle 1 Day 1 to EOC -3	Day -3 to EOC		X

[a] The scheduled day is relative to Day 1 of each cycle.

Note: The end date of a cycle (EOC) is defined as one day earlier than the date of Day 1 study drug administration of its next cycle. For the last cycle (where no subsequent cycle is given), the end of cycle will be defined as the last dose of the last cycle.

EOC = end of cycle.

## 7.7. SOFTWARE VERSION

All analyses will be conducted using SAS® version 9.4 or higher.

## 7.8. DATA HANDLING CONVENTIONS

Data will be summarized by dose level (Stage 1), malignancy type (Stage 2), and overall as appropriate. Some summary results (efficacy) for Stage 1 may be also presented by malignancy type (e.g., for any interim looks).

Continuous assessments will be summarized by number of patients (n), mean, standard deviation, median, minimum, and maximum. The decimal places for minimum and maximum will be the same as the max decimal places in original data. Mean and Median will keep one

HMPL-523

more decimal place than the decimal places in original data; standard deviation will keep 2 more decimal places than the decimal places in original data, but no more than 4 decimal places. For categorical variables, descriptive statistics will include the number and percentage of patients for each category. The denominator for all percentages will be the number of patients in that treatment group or malignancy type within the population of interest, unless otherwise noted. The percentage will keep one decimal places. If the percentage is 100%, 100% will be reported; if the frequency is 0, no percentage will be reported. Fractional numeric values will be presented with a zero to the left of the decimal point (for example, 0.12 – 0.30, not .12 – .30). If needed, the 2-sided 95% confidence interval for percentage will be calculated using Clopper-Pearson method (Clopper, C. J., & Pearson, E. S. 1934) as well, and the decimal places will be the same as percentage.

Time to event variable will be analyzed using Kaplan-Meier method and summarized with median, 25% and 75% percentiles with their corresponding 95% confidence intervals (CI) which are calculated from a log-log transformation based on the method by Brookmeyer (Brookmeyer, R., & Crowley, J. 1982).

## 7.9. MISSING DATA

In general, all available data will be included in the analyses. Unless otherwise specified, there will be no substitution of missing data, i.e. missing data will not be replaced but will be handled as 'missing' in the statistical evaluation. Partial dates may be imputed for statistical analyses for specific outcomes. In such cases, the specific imputation rules are provided below. However, as a global convention, imputed dates should not be shown in listings.

### Adverse Events

If the adverse event onset date is missing or partial, the date will be compared as far as possible with the date of first dose of study medication. Adverse events will be assumed to be treatment-emergent, unless there is clear evidence (through comparison of partial dates) to suggest that the adverse event started prior to the first dose of study medication or more than 30 days after last dose of study medication or new antineoplastic therapy.

### **Missing or partial start dates:**

- If the date has no missing year and month but the day is missing:
  - 1) If the year and month of first dose date are the same as the year and month of the start date, then the date of first dose will be used.
  - 2) Otherwise, 1st day of the month will be used.
- If the date has no missing year, but has missing month, and the year of first dose date is the same as the year of the start date, the date of first dose will be used.
- If the date has no missing year, but has missing month, and the year of first dose is

HMPL-523

- o not the same as the year of the start date, then January 1st will be used.
- o If the start date is completely unknown, then use the date of first dose.

**Missing or partial stop dates:**

- o If the date has no missing year and month but the day is missing, then use the last day of the month.
- o If the date has no missing year, but has missing month, then use December 31st of that year.
- o If the stop date is completely unknown, do not impute the stop date.

Note: For patients who died, if the imputed start/stop date is later than date of death, the imputed date will set to be date of death.

**Concomitant Medications/Procedures**

If concomitant medication start and/or stop dates are missing or partial date, the dates will be compared as far as possible with the date of first dose of study medication. Medications will be assumed to be concomitant, unless there is clear evidence (through comparison of partial dates) to suggest that the medication started prior to the first dose of study medication. If there is clear evidence to suggest that the medication started prior to the first dose of study medication, the medication will be assumed to be Prior and Concomitant, unless there is clear evidence to suggest that the medication stopped prior to the first dose of study medication. If there is clear evidence to suggest that the medication stopped prior to the first dose of study medication, the medication will be assumed to be prior.

**Missing or partial start dates:**

- o If the date has no missing year and month but the day is missing, the 1st day of the month will be used.
- o If the date has no missing year, but has missing month, then January 1st will be used.
- o If the start date is completely unknown, do not impute the start date.

**Missing or partial stop dates:**

- o If the date has no missing year and month but the day is missing, then use the last day of the month.
- o If the date has no missing year, but has missing month, then use December 31st of that year.
- o If the stop date is completely unknown, do not impute the stop date, and assign

HMPL-523

‘ongoing’ status.

Note: For patients who died, if the imputed start/stop date is later than date of death, the imputed date will set to be date of death.

### **Death Date**

- If year and month of death date are known but the day is unknown, day will be imputed as 15 (for example, if a patient is reported to die on December 2017, the death date will be imputed as 15 December 2017).
- If only year are known, death date will be imputed as 1st July of the given year.
- If the imputed death date is prior to the last known alive date, then the death date will be imputed as last known alive date+1.
- If death date is totally missing, dates will be imputed as the last known alive date + 1.
- Last known alive date could be derived from the latest date from:
  - Adverse event start/stop dates
  - Concomitant medication start/stop dates
  - Concomitant procedure start/stop dates
  - Subsequent therapies start dates
  - HMPL-523 treatment start/end dates
  - Tumor scan dates
  - PET-CT examination dates
  - Laboratory sample collection dates
  - ECG dates
  - Vital signs assessment dates
  - ECOG assessment dates
  - Physical examination dates
  - ECHO assessment dates
  - End of Treatment date
  - End of Study date (exclude lost to follow up reason)

Note: if the imputed death date is after the end of study date, then the death date will be imputed as the end of study date.

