### **Progression free survival (PFS)**

PFS is defined as the time (in months) from the date of first study medication to the earliest date of disease progression or death due to any reason whichever occurs first.

HMPL-523

PFS (months) = ([date of progression or death or censoring] - [date of first dose of study medication] + 1)/30.4375.

A patient is deemed to be censored according to the rules specified in **Error! Reference source not found.** below.

Error! Reference source not found.: **Progression-Free Survival Censoring Rules**

#	Situation	Date of Progression or Censoring	Outcome	Event/Censor reason
1	Death (without previously documented progressive disease [PD]) within two evaluable tumor assessments [a] from last evaluable tumor assessment or first dose (if no post-baseline tumor assessment)	Date of death	Event	Death
2	Death (without previously documented PD) after two or more consecutive missed/non-evaluable tumor assessments [a] from last evaluable tumor assessment or first dose (if no post-baseline tumor assessment)	Date of last evaluable tumor assessment or date of first dose (if no post-baseline tumor assessment)	Censored	Death after two or more consecutive missed or NE tumor assessments
3	Progression within two evaluable tumor assessments [a] from last evaluable tumor assessment or first dose (if no post-baseline tumor assessment before PD)	Date of progression	Event	Disease Progression
4	Progression after two or more consecutive missed/non-evaluable tumor assessments [a] from last evaluable tumor assessment or first dose (if no post-baseline tumor assessment before PD)	Date of last evaluable tumor assessment or date of first dose (if no post-baseline tumor assessment before PD)	Censored	Progression after two or more consecutive missed or NE tumor assessments
5	Progression after new anti-cancer treatment	Date of last evaluable tumor assessment before new anti-cancer treatment or date of first dose (if no post-baseline tumor assessment before new anti-cancer)	Censored	Progression after new anti-cancer therapy
6	No baseline tumor evaluable assessment and alive	Date of first dose	Censored	No baseline assessment
7	No post-baseline tumor evaluable assessment and alive	Date of first dose	Censored	No post-baseline assessment

HMPL-523

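### SAP 7.9 sets a partial or missing death date to the End-of-Study date for any patient with a complete End-of-Study date and a reason other than lost to follow-up, so its 15th-of-month and 1 July rules never decide the date

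*SAP*

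**What the plan says.** SAP 7.9, under Death Date, sets out a chain of rules.

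- Day missing: "If year and month of death date are known but the day is unknown, day will be imputed as 15". The SAP's own example turns December 2017 into 15 December 2017.
- Month missing: "If only year are known, death date will be imputed as 1st July of the given year".
- Floor: "If the imputed death date is prior to the last known alive date, then the death date will be imputed as last known alive date+1". A completely missing date is also set to the day after the last known alive date.
- The last known alive date is the latest of a list of contact dates. One entry is "End of Study date (exclude lost to follow up reason"). No other EOS reason is excluded, so an EOS closed because of death stays in. The End of Treatment date is listed with no exclusion at all.
- Closing note: "if the imputed death date is after the end of study date, then the death date will be imputed as" the EOS date.

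Nothing in the section keeps the result inside the recorded month or year.

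The date is used in SAP 16.1.1. Row 1 of the PFS censoring table counts as an event a "Death (without previously documented progressive disease [PD]) within two evaluable tumor assessments" of the last evaluable scan. Row 2 censors a death that follows two or more missed assessments. DoR also ends at death and is censored by the PFS rules.

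**The concern.** The floor and the cap work against each other. If the EOS date is one of the dates that prove a patient was alive, the floor pushes an earlier imputed death past EOS and the cap then pulls it back to EOS. The rules meant to respect the recorded month or year are left with no effect.

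The authors saw the principle for lost to follow-up, where the EOS date is not evidence of life. The same holds when EOS was closed because the patient died, but that case is not excluded.

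At stake is the event date for PFS and DoR, and whether a death falls in row 1 (event) or row 2 (censored). Preliminary efficacy in the expansion stage is a primary objective. Protocol Table 2 shows HL with 25 patients and the other enrolled cohorts with 1 to 9. One reclassified death is visible on a Kaplan-Meier curve of that size.

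**Working it through.** **Notation (all rules from SAP 7.9, Death Date).** D0 is the date from the 15th or 1 July rule, L the last known alive date, E the EOS date and D the final date. The rules are applied in the written order, with the closing note last.

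**General result, EOS reason other than lost to follow-up, E complete.** E is in the list, so L ≥ E.

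- D0 missing, or D0 < L: D = L + 1 > E, so the cap gives D = E.
- D0 ≥ L: then D0 ≥ E. Either D0 = E already, or D0 > E and the cap gives D = E.

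Every path ends at E. The order of the rules does not rescue the 15th or 1 July: with the cap before the floor, the result is E or L + 1.

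**The SAP's own example.** The day-missing rule alone reproduces 15 December 2017. The full chain for a death recorded as December 2017, with other contacts assumed to run to 4 December 2017 (20 November in the last row), gives:

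| EOS date | After floor | After cap | Recorded month kept? |
|---|---|---|---|
| 15 Dec 2017 | 15 Dec 2017 | 15 Dec 2017 | yes |
| 28 Dec 2017 | 29 Dec 2017 | 28 Dec 2017 | yes |
| 20 Jan 2018 | 21 Jan 2018 | 20 Jan 2018 | no |
| 20 Apr 2018 | 21 Apr 2018 | 20 Apr 2018 | no |
| 20 Nov 2017 | 15 Dec 2017 | 20 Nov 2017 | no |

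The example survives only when EOS is itself 15 December.

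**Lost to follow-up.** Here E is not in L. With L = 4 December and E on or after 15 December, the result is 15 December, as intended. In the last row the cap still pulls the death back to 20 November, out of its recorded month.

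**Effect on PFS (assumed dates).** First dose is 1 July 2017 and the last evaluable scan 20 October 2017. The scan is on study day 112, below 120, so the SAP's two-missed-assessments limit is 126 days. PFS in months = (date − first dose + 1)/30.4375.

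- Death on 15 Dec 2017: 56 days after the scan, event at 168/30.4375 = 5.52 months.
- Reset to EOS 20 Jan 2018: 92 days, event at 204/30.4375 = 6.70 months.
- Reset to EOS 20 Apr 2018: 182 days > 126, censored at the scan, 112/30.4375 = 3.68 months.

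**The opposite direction (assumed dates).** The last scan is 20 Feb 2022, EOS is 10 Mar 2022 by withdrawal, and death is recorded as September 2022. D0 = 15 Sep is later than L, and the cap sets 10 Mar, which is 189 days earlier. That is 18 days after the scan, so an event. At 15 Sep the gap is 207 days, beyond all three SAP limits (126, 154 and 182), so the death would be censored.

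**The case against.** The strongest case is that this will rarely matter.

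- **Few patients qualify.** A patient must have an incomplete death date, no earlier documented progression and no earlier new anti-cancer therapy. No such patient is shown, and there may be none. This stands.
- **Incomplete dates should be uncommon.** Protocol 6.4.6 and 6.5 require prompt reporting of on-study deaths not due solely to the malignancy. Deaths due solely to it go on the completion/discontinuation form, and discrepant data are queried. This also stands.
- **EOS may be the death date.** If sites enter it so, returning EOS is correct. The documents do not say that they do: SAP 9.1 takes the reason for leaving the study from the EOS form, while SAP 17.3 takes deaths from a separate page. Neither reading can be proved.
- **Late deaths are seldom collected.** Protocol 6.7 asks for deaths after study participation only if felt related to the drug, so the September 2022 illustration is less likely than the late-closing EOS.
- **The list is permissive.** The SAP says the last known alive date could be derived from it, so a programmer might omit EOS. But EOS is expressly named.
- **Consequences are limited.** This is a single-arm Phase I study with no test of PFS. Response rates rest on tumor assessments, not on the death date.

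These points limit the size of the effect. They do not restore the 15th or 1 July rule.

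**Conclusion.** The SAP is wrong as written. For a patient with a complete EOS date and any reason other than lost to follow-up, a partial or missing death date always becomes EOS. The recorded month or year is contradicted when EOS falls outside it. For patients lost to follow-up, the cap alone pulls a death recorded in a later month back to EOS.

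The result follows from the text and assumes only that the listed EOS date is used and the note is applied last. A missing or partial EOS date is outside it. The month figures above rest on invented dates and show direction only. The number of affected patients is unknown and probably small. That makes this a correction to make before lock, not a threat to the study.

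Two stronger readings are not supported.

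- A reader might infer that PFS and DoR are distorted generally. Complete death dates are untouched, as are patients with earlier progression or new therapy, and no count of incomplete dates is given.
- A reader might also infer circularity, because adverse-event and medication dates feed the last known alive date and are themselves cut back to death "if the imputed start/stop date is later than date of death". This arises only if imputed dates enter the list. The SAP does not say they do, and its general rule in 7.9 is no substitution unless specified.

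**What to change.** Amend the Death Date rules in SAP 7.9:

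1. Exclude the EOS and End of Treatment dates from the last known alive list when their reason is death, as is already done for EOS with lost to follow-up. State that the list uses only recorded, non-imputed dates. This also settles the circularity question.
2. Use the 15th or 1 July, or the day after the last known alive date if later, and keep the result within the recorded month or year. If a genuine contact falls after that period, query the site rather than impute.
3. Apply the EOS cap only when the EOS reason is death, after steps 1 and 2, and without moving the date out of the recorded month or year. Otherwise drop it.

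With EOS closed for death on 28 December 2017, 20 January 2018 or 20 April 2018 and contacts to 4 December, these rules return 15 December 2017, matching the SAP's example.

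The cost is a wording change and one derivation, with no new data collection beyond any site query. SAP section 2 allows revision before the final database lock.

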### **Last dose date**

#### **Missing or partial date of last dose date of study treatment:**

- If the date is partially missing, then impute the date as the last day of given part of original last dose date. If the day is missing, imputed date will be the last day of the month of the partial last dose. If the month is missing, imputed date will be the last

---

HUTCHMED Ltd.

CONFIDENTIAL

HMPL-523

day of the year of the partial last dose. If the imputed date is after the end of study date, then it will be replaced with the end of study date.

- If the date is completely missing, then impute the date at end of study date.

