4 STUDY DESIGN

4.1 Description of Study

This is a Phase I, open-label, multicenter study of HMPL-523 administered orally to patients with relapsed or refractory lymphoma who have exhausted approved therapy options.

The study consists of a dose escalation stage (Stage 1) and a dose expansion stage (Stage 2). Both stages include a screening period, a treatment period, and a follow-up period. The screening period starts when the patient has provided written informed consent and ends immediately prior to initiation of study drug administration on Day 1 of Cycle 1. The treatment period begins on Day 1 of Cycle 1 and concludes on the final day of study drug administration. The follow-up period begins at the end of treatment and continues until the patient experiences disease progression, starts a new anticancer therapy, or dies, or the sponsor has concluded the study.

The start of the clinical study is defined as the date the study is open for recruitment at any site. This date was 21 February 2019. The start of the clinical study in EU is defined as the date the clinical study is open for recruitment at the first clinical study site within an EU Member State. This date was 05 September 2019.

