5.7 Participant Completion/Discontinuation

5.7.1 Study Completion/Early Termination Visit

Patients who complete the study or discontinue from the study early will be asked to return to the clinic at 30 ± 7 days after the last HMPL-523 administration for a follow-up visit. Ongoing TEAEs thought to be related to HMPL-523 will be followed until the event has resolved to baseline grade, the event is assessed as stable by the investigator, new antitumor treatment is initiated, the patient is lost to follow-up, the patient withdraws from the study, or it has been determined that the study treatment or participation is not the cause of the AE, whichever comes first.

Follow-up (Extended Monitoring)

Patients who discontinue the study drug due to reasons other than disease progression will remain on the study and will be followed quarterly for tumor assessment until the patient has the first progression, starts new anticancer therapy, dies, or until 12 months after the initial dose with the study drug. The assessments to be performed at the follow-up visits are listed in the Schedule of Activities in [Appendix 1](#).

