### 9.1. DISPOSITION

Patient disposition, discontinuation as well as reasons for discontinuation will be presented for the all enrolled set. The number of patients who provided informed consent for the study will be summarized. Screen failed patients and the reason for screen failure as well as patients who passed screening but withdrew before study treatment will also be summarized.

The number and percentage of patients who completed, discontinued or were still on the treatment will be presented. Reasons for discontinuation from study treatment as recorded on the “End of Treatment (EOT)” form will be summarized. The number and percentage of patients who have completed, discontinued or were still on study will be presented. Reasons for discontinuation from study as recorded on “End of Study (EOS)” form will be summarized. The follow up time will be also summarized with mean, median, and standard deviation.

Follow up time (days) = the latest date in database – the first dose date + 1. For the interim evaluation of Stage 1 results, follow-up time (days) is defined as date of cutoff (even if patient was off treatment or died after the cutoff date) – first dose date +1.

In addition, number and percentage of patients with <6, >=6, <12, >=12 months follow-up time will be summarized.

The number/percentage of patients included in FAS, RES, DEAS (stage 1 only), and PKAS will be summarized for both Stage 1 and Stage 2. A by-patient listing will include the inclusion/exclusion of patients in each analysis set.

Individual listings containing the site and patient number, informed consent information, first and last study medication administration date, treatment discontinuation information and end of study information will be provided separately for Stage 1 and Stage 2. A separate data listing will include eligibility for study entry based on inclusion/exclusion criteria.

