## 15. STUDY MEDICATION EXPOSURE AND COMPLIANCE

Exposure to study medication in days will be summarized based on the FAS.

The date of first study medication administration will be taken from the "HMPL-523 Treatment" eCRF form. The date of last study medication will be taken from the last study medication administration date.

Study drug interruptions, compliance, and dose changes are not taken into account for duration of exposure.

The following study medication administration summaries will be reported for this study:

- Number of cycles: the number of cycles in which the patient took any dose of study medication.
- Total duration exposure (months):

$$\text{Total duration of treatment (months)} = \left( \frac{\text{date of last dose} - \text{date of first dose} + 1}{30.4375} \right)$$

It will be summarized as continuous variables and also categorized into groups as below:

- < 6 months exposure
  - $\geq 6$  to < 12 months exposure
  - $\geq 12$  months exposure
- Actual duration of study treatment (months):

Actual duration of study treatment is defined as the total number of months on the study medication during the treatment phase (excluding the periods of dose discontinuation or dose interruptions).

- Cumulative dose (mg):

Cumulative dose (mg) is defined as the sum of the total doses patient actually received during an exposure period.

HMPL-523

- Dose intensity (mg/day):

$$\text{Dose intensity (mg/day)} = \left( \frac{\text{Cumulative dose (mg)}}{\text{total treatment exposure(days)}} \right)$$

- Relative dose intensity (%):

$$\text{Relative dose intensity (\%)} = \left( \frac{\text{dose intensity (mg/day)}}{\text{planned dose intensity(mg/day)}} \right) * 100$$

The planned dose intensity is defined in the protocol for each cohort: 100mg/day, 200mg/day, 400 mg/day, 600 mg/day, 700 mg/day, and 800 mg/day.

It will be summarized as continuous variables and also categorized into groups as below:

- < 50%
- 50% - <70%
- 70% - <90%
- 90% - <110%
- $\geq$ 110%

The number and percentage of patients with any dose modification will be presented. Dose modification will be further characterized by presenting the numbers and percentages of patients with any dose reduction, dose escalation and dose interruption. Reasons for dose adjustments will be summarized as well.

Details of study treatment administration will be included in patient listings.

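### SAP 7.9 sets a missing last-dose date to the end of study, though patients can be on study off drug; for any such patient exposure is overstated by about 1 to 11 months and the safety windows lengthen with it

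*SAP*

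**What the plan says.** SAP 7.9, under Last dose date, gives two rules. A partial date is moved to the last day of the known month or year, with one limit: "If the imputed date is after the end of study date, then it will be replaced with the end of study date". For a wholly missing date: "If the date is completely missing, then impute the date at end of study date". SAP 9.1 reads study discontinuation from each patient's End of Study form, so I take the end-of-study date to be the patient's own.

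SAP 15 takes the date from dosing data: "The date of last study medication will be taken from the last study medication administration date". Total exposure is last dose minus first dose plus one, divided by 30.4375. Dose intensity divides the doses actually received by total exposure in days.

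The protocol separates stopping drug from leaving the study. Section 5.7.1 states: "Patients who discontinue the study drug due to reasons other than disease progression will remain on the study". They are seen quarterly until progression, new therapy, death, or "until 12 months after the initial dose with the study drug". Section 5.7.3 also says that stopping treatment is not stopping the study. Section 4.1 describes follow-up with no 12-month limit: "The follow-up period begins at the end of treatment and continues until the patient experiences disease progression, starts a new anticancer therapy, or dies", or until the sponsor concludes the study.

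**The concern.** The end-of-study date is the latest date the last tablet could have been taken, not a likely one. For a patient who stops early for a reason other than progression, it can be months too late. Closer information exists. SAP 7.9 lists treatment end dates, subsequent-therapy start dates and an End of Treatment date among the sources for the last-known-alive date, and it caps imputed AE and medication dates at death. The last-dose rule uses none of these.

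The last-dose date feeds total exposure and the dose-intensity denominator (SAP 15), the 30-day TEAE limit (SAP 17.2), the 37-day on-treatment period and worst laboratory grade (SAP 7.3, 17.4), the concomitant-medication window (SAP 14.1), the end of the last cycle (SAP 7.6) and the imputed start of new therapy (SAP 7.9). Most Stage 2 cohorts are small (Protocol Table 2: post-BTK CLL 7, PTCL 9, several of 1 or 2), so a single patient can move a cohort summary.

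**Working it through.** The documents give no figure for the effect of this rule, so there is nothing to reproduce. I applied the SAP's own formulas.

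**Inputs**
- Planned dose in Stage 2: 700 mg/day (SAP 4.1.2).
- End of study: 30 or 37 days after last dose for a patient who leaves at the 30 ± 7 day visit (Protocol 5.7.1), otherwise an assumed Day 182, or Day 365 for the 12-month limit.
- Last-dose days are assumed, for illustration. Day 1 is the first dose.

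**Formulas**
- Exposure (months) = last-dose day / 30.4375
- Overstatement = (end-of-study day − last-dose day) / 30.4375
- RDI, if only recorded doses count = (700 × last-dose day / end-of-study day) / 700
- TEAE window closes at last dose + 30 days

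| True last dose (day) | End of study (day) | True exposure (months) | Imputed exposure (months) | Overstated by (months) | RDI, recorded doses only | TEAE window closes: true / imputed |
|---|---|---|---|---|---|---|
| 28 | 365 | 0.92 | 11.99 | 11.07 | 7.7% | Day 58 / 395 |
| 56 | 86 | 1.84 | 2.83 | 0.99 | 65.1% | Day 86 / 116 |
| 56 | 93 | 1.84 | 3.06 | 1.22 | 60.2% | Day 86 / 123 |
| 56 | 182 | 1.84 | 5.98 | 4.14 | 30.8% | Day 86 / 212 |
| 60 | 365 | 1.97 | 11.99 | 10.02 | 16.4% | Day 90 / 395 |
| 168 | 365 | 5.52 | 11.99 | 6.47 | 46.0% | Day 198 / 395 |
| 336 | 365 | 11.04 | 11.99 | 0.95 | 92.1% | Day 366 / 395 |

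**The Day 60 row in full**
- Exposure: 60/30.4375 = 1.97 months becomes 365/30.4375 = 11.99 months. The SAP 15 category moves from under 6 months to 6 to under 12.
- If cumulative dose counts only recorded doses: 700 × 60 = 42,000 mg, and 42,000/365 = 115 mg/day, so RDI is 115/700 = 16.4% instead of 100%.
- If the open dosing record is filled to the imputed date: 700 × 365 = 255,500 mg instead of 42,000 mg, and RDI stays at 100%.
- On-treatment period: ends on Day 365 + 37 = 402 instead of Day 60 + 37 = 97.
- Effect on a cohort mean: 10.02/7 = 1.43 months in a cohort of 7, or 10.02/25 = 0.40 months in the Hodgkin cohort of 25.

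The window dates assume that no new anticancer therapy starts first. An earlier start closes both windows (SAP 7.3, 17.2), but does not shorten exposure.

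**Partial dates.** If only the day is missing, the error is at most 30 days. If the month is missing, year-end is used, and again only end of study limits it.

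**The case against.** The best defence is that the trigger may never occur. Dosing times go into a patient diary (Protocol 5.3.4), drug is accounted for (5.3.3), and discrepant data are queried and source-verified (11.1, 11.2). That stands: the number of missing dates is not given and may be zero. The rule is also sensible for a patient still on drug at study end.

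Extended follow-up already stops at progression, new therapy or death, so end of study should often lie close to those dates. That stands too, and it leaves the End of Treatment date as the most useful bound. The case report form is not available, so that date might record a decision or a visit rather than the last tablet; it would still normally be closer than end of study.

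For safety, a late last-dose date includes too many events rather than hiding any, in line with the SAP's habit of calling doubtful events treatment-emergent. Appendix 1 of the protocol marks no AE or routine laboratory collection at the quarterly visits, although Section 6.3.1 collects AEs until 30 days after last dose or study discontinuation, whichever is later. So few late events may enter. This does not help exposure, which is simply too long.

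Three stronger readings are tempting, and the documents do not support them:
- A reader might infer that dose intensity must collapse. It does so only if cumulative dose stops at the recorded doses; filling the open record leaves it near 100% and inflates cumulative dose instead.
- A reader might infer that the TEAE window always runs to about Day 395. That needs an early stop for a reason other than progression, then no progression, new therapy or death through Day 365.
- A reader might infer that the RP2D is undermined. It was already set at 700 mg from escalation data (Protocol 4.4.5), and DLTs use a fixed 28-day window that does not depend on last dose.

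**Conclusion.** The rule as written is wrong for any patient who was off drug before end of study and whose last-dose date is missing or partial in a way that lets the imputed date overshoot. For a wholly missing date, exposure is overstated by about 1 month after an exit at the 30 ± 7 day visit, and by about 11 months after a very early stop for a reason other than progression with follow-up to Day 365. The TEAE and on-treatment windows move by the same number of days unless new therapy starts earlier. Either dose intensity is too low or cumulative dose is too high; the SAP does not settle which.

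The upper figure rests on the 12-month limit in Protocol 5.7.1. If follow-up ran under Section 4.1, which states no such limit, it could be larger. The matter is minor: it may touch no patient, the affected summaries are descriptive, and RP2D and DLT conclusions stand. It is worth correcting because the cost is trivial and the cohorts are small.

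**What to change.** In SAP 7.9, replace the last-dose rule so that a missing or partial date is imputed as the earliest of:
- the recorded End of Treatment date;
- the day before a recorded start of new anticancer therapy;
- the date of death;
- the end-of-study date;
- the last day of any recorded month or year.

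The result must never be earlier than the last recorded dosing entry. The new-therapy bound must use recorded dates only: SAP 7.9 imputes a wholly missing start, and some partial ones, as last dose + 1, so each date would otherwise define the other.

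In SAP 15, state that the same date closes the final dosing record for cumulative dose and sets the exposure denominator.

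The cost is a sentence in each section and a small programming change. It needs no new data, provided the End of Treatment date is collected as the SAP's own list indicates. SAP 2 allows revision before final database lock. If no dates are missing, no result changes.
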